14.3 Subgroup analyses

Subgroup analyses will be performed regarding:

1. Height of the tumour:

- hypothesis is higher rate of involved CRM in the laparoscopic group in tumours 0-5cm from the anal verge compared with the TaTME group

- hypothesis is higher rate of local recurrence in the laparoscopic group in tumours 0-5cm from the anal verge compared with the TaTME group

2. Stage of disease:

- hypothesis is better disease-free and overall survival in patients with stage III disease compared with patients with stage I or stage II disease in the TaTME group as well as the laparoscopic group

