14 STATISTICS AND DATA ANALYSIS

14.1 Sample size calculation

The primary endpoint is the local recurrence after 3 years. In laparoscopic TME the percentage of local recurrence is estimated 5%. A local recurrence increase of 4% is believed to be inferior. Based on this difference, sample size calculation has been done with a one-sided level of significance of 2,5% and a power of 80%. A total of 1104 patients is needed, 735 patients in the TaTME arm and 369 patients in the laparoscopic TME arm.

In this sample size calculation, additional postrandomisation analyses (drop-out, cross-over total 5%), is taken into account.

Randomisation will be stratified for

- T3a and less / T3b and more
- Downstaged with chemoradiotherapy: yes / no / NA
- Preoperative radiotherapy: yes / no
- Height of the tumour: 0-2.0cm / 2.1-5.0cm / 5.1-10cm
- Gender: male / female
- BMI \leq 30.0 / BMI $>$ 30.0

The randomisation will be executed in such a way that concealment of allocation for the indicating surgeon is guaranteed.

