14.2 Statistical analysis plan

Baseline numerical data will be described in means, standard deviations or medians and interquartile ranges, baseline categorical data will be displayed in percentages. All comparative analyses will be conducted on an 'intention to treat' basis. Consequently, patients who are randomised to TaTME and converted to a laparoscopic or open TME, will be analysed in the TaTME group. Patients who are randomised to a laparoscopic resection and converted to TaTME or open TME, will be analysed in the laparoscopic group. Ninety days postoperative mortality, pathological resection margin and complication rates will be compared using the Chi-square test or an exact test if necessary. Local recurrence rate, disease-free and overall survival will be compared using the Log-rank test. Exploratory analysis of the prognostic effects of various baseline factors on disease-free survival will be carried out through multivariate Cox-regression. Apart from intention to treat analyses, per protocol analyses will be applied.

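### The stage subgroup item in Protocol section 14.3 compares stage III with stage I–II inside each arm, with the advanced stage expected to do better, and does not compare TaTME with laparoscopic TME

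*Protocol*

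**What the plan says.** Protocol section 14.3 (Subgroup analyses) names two topics.

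- **Height of the tumour.** Two hypotheses are given, one on involved circumferential margin and one on local recurrence. Both set the arms against each other in low tumours. The second reads: "hypothesis is higher rate of local recurrence in the laparoscopic group in tumours 0-5cm from the anal verge compared with the TaTME group".
- **Stage of disease.** One hypothesis is given: "hypothesis is better disease-free and overall survival in patients with stage III disease compared with patients with stage I or stage II disease". The sentence ends "in the TaTME group as well as the laparoscopic group".

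Section 14.2 (Statistical analysis plan) bears on the same outcomes in two places. The general comparison is: "Local recurrence rate, disease-free and overall survival will be compared using the Log-rank test". A separate prognostic analysis is also planned: "Exploratory analysis of the prognostic effects of various baseline factors on disease-free survival will be carried out through multivariate Cox-regression".

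Section 5.1 admits AJCC stages 1 to 3, including downstaged tumours. Section 15.2 records clinical TNM stage at randomisation, and section 15.5 records pathological stage after surgery. Section 14.3 does not say which of the two defines the stage subgroups.

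**The concern.** A subgroup analysis in a randomised trial asks whether the effect of treatment differs between kinds of patient. The stage item does not ask this. It predicts how patients at one stage will fare against patients at another, and makes the same prediction in both arms. Patients are not randomised to a stage, so this is an observational prognostic contrast.

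The predicted direction is also odd. Stage III is the most advanced stage the trial admits, yet it is expected to have the better survival, and the protocol gives no reason for this.

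What is at stake is one prespecified secondary analysis. An analysis plan that follows section 14.3 faithfully inherits a hypothesis that does not bear on the two operations. One that departs from it contradicts the protocol. If the wording is repaired only after outcomes are known, the new hypothesis will look data-driven.

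**Working it through.** The stage item contains no figure, so the check is mainly one of logic and of setting sections side by side.

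**1. What each item contrasts**

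| Item | Groups compared | Held fixed | Arms compared? |
|---|---|---|---|
| 14.3, height | Laparoscopic v TaTME | Tumour at 0–5 cm | Yes |
| 14.3, stage | Stage III v stage I–II | Arm | No |
| 14.2, log-rank | Laparoscopic v TaTME | Nothing | Yes |
| 14.2, Cox | Levels of baseline factors | Not stated | Not its purpose |

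The stage item departs from the pattern of the height item in the same section.

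**2. What the stage contrast can reveal**

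Let S(a, s) be the outcome in arm a (T = TaTME, L = laparoscopic) and stage group s, on any additive scale, such as survival at three years or log hazard.

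- The item concerns D(T) = S(T, III) − S(T, I–II) and D(L) = S(L, III) − S(L, I–II). It predicts that each favours stage III.
- The treatment effect in stage s is E(s) = S(T, s) − S(L, s).
- If TaTME shifts the outcome by the same amount c in every stage, D(T) becomes [S(T, III) + c] − [S(T, I–II) + c], which is unchanged. The item is blind to a treatment effect common to all stages, whatever its size or sign.
- The interaction is E(III) − E(I–II), which rearranges to D(T) − D(L). The item predicts the direction of D(T) and of D(L) separately and does not take their difference. Both predictions could be right, or both wrong, with an interaction in either direction or none.

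**3. Direction**

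Section 5.1 uses AJCC staging, in which a higher stage is more advanced disease. The protocol never says in words that stage III has the worse prognosis, so the judgement that the direction is reversed rests on that ordering. No other section restates or corrects the hypothesis.

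**4. Overlap with section 14.2**

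If the item is read as prognostic, the Cox regression already covers this kind of question for disease-free survival. The overlap is partial: the Cox analysis is not stated for overall survival, and its baseline factors are not listed, so stage is presumed to be among them.

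**5. Does anything confirmatory depend on it?**

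Inputs from section 14.1 and the Trial Summary: 5% local recurrence at three years in the control arm, a margin of 4 percentage points, one-sided 2.5% significance, 80% power, 2:1 allocation and 5% loss. Assuming equal true rates:

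- Control n = (1.960 + 0.842)² × 0.05 × 0.95 × (1 + 1/2) / 0.04², which rounds up to 350. The TaTME arm is 2 × 350 = 700, and the total is 1050.
- Allowing for 5% loss: 1050 / 0.95 = 1105.3, so 1106. The simpler 1050 × 1.05 gives 1103. The stated total is 1104 (735 + 369).
- With 95% of 735 + 369 evaluable, power is 80.1%.

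The stated size reproduces to within two patients, and stage enters nowhere in it.

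**The case against.** The strongest reply is that this is a drafting slip in a minor item. The stages may have been transposed, or a between-arm hypothesis may have been garbled. No significance level is allotted to section 14.3, and the randomised comparison of disease-free and overall survival is secured by section 14.2. Anyone who estimated the stage contrast in both arms would also hold the ingredients of the interaction. Interaction models, interval estimates and an exploratory label are commonly left to a statistical analysis plan, which is not shown here.

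Most of that stands, and it rules out several stronger readings that a reader might infer:

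- **That effect modification by stage will go untested.** Silence in the protocol does not show this. The text supports only that the stated hypothesis is not a treatment comparison.
- **That a subgroup test is used up, or that the hypothesis is bound to be refuted.** No alpha is assigned, and the protocol gives no stage-specific survival figures from which such a probability could be worked out.
- **That the height item is equally faulty.** It compares the arms. Naming a hypothesis for 0–5 cm does not say that 5.1–10 cm goes unanalysed. Section 14.3 names no test, so a warning about p-values within a subgroup has no text behind it.

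The reply does not rescue the stage item. A slip still needs correcting, and this is more than detail left for later: the protocol itself fixes the groups and the direction, and nothing elsewhere overrides them.

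**Conclusion.** The point holds for the stage item alone. As written it is a within-arm prognostic contrast, stated in the reverse of the AJCC ordering, which cannot inform the comparison of TaTME with laparoscopic TME and partly repeats the exploratory Cox analysis.

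Its size is one secondary subgroup hypothesis. No number in the protocol changes, and no primary or confirmatory conclusion is affected. It is worth correcting before outcome data are examined because the correction costs so little.

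The conclusion rests on the plain reading of section 14.3 and, for direction only, on the ordering of AJCC stages. What the authors meant cannot be settled from the protocol, so two repairs are open.

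**What to change.** Choose one, according to intent.

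1. **If a subgroup analysis was meant**, replace the stage hypothesis with the effect of TaTME versus laparoscopic TME on disease-free and overall survival within clinical stage I–II and within stage III. Report estimates with 95% confidence intervals and a treatment-by-stage interaction test, and label the analysis exploratory. Define stage by the clinical TNM recorded at randomisation (section 15.2). Pathological stage (section 15.5) is determined after the operation under study, so grouping by it would weaken the protection of randomisation.
2. **If a prognostic statement was meant**, correct its direction and move it to the prognostic analysis in section 14.2, adding overall survival there if that outcome is wanted.

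The cost is a few lines of wording. The first option adds two interaction models, one per outcome, on data already collected. Neither option touches the sample size.

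Optional, and not the correction of an error: report the height effect at both 0–5 cm and 5.1–10 cm with an interaction test. Height is already a stratification factor in section 14.1, where the two lower strata together make up 0–5 cm.

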5 ELIGIBILITY CRITERIA

5.1 Inclusion criteria

- 1) Solitary adenocarcinoma rectal cancer within 10 cm from anal verge defined by MRI
- 2) Stage 1-3 according to the AJCC classification including downstaged tumours based on adequate imaging of the thorax and abdomen
- 3) Intention for LAR with colorectal anastomosis or with coloanal anastomosis
- 4) Suitable for elective laparoscopic surgical resection
- 5) Informed consent according to local requirements

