15.2 Data collected at randomisation

At randomisation, the clinician will be asked to give the following information through the internet:

- Eligibility criteria fulfilled?
- Randomising physician/surgeon
- Hospital (+ fax number)
- Type of planned surgery
- Patient: gender
- Patient: date of birth
- Clinical TMN stage

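### The stage-of-disease subgroup hypothesis (14.3, item 2) is stated in reverse and contrasts stages within each arm, not TaTME with laparoscopic TME

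*Protocol*

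**What the plan says.** Protocol section 14.3 lists two subgroup analyses.

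- Item 1, tumour height, has two hypotheses, one on involved CRM and one on local recurrence. Both compare the operations within low tumours. The second reads: "hypothesis is higher rate of local recurrence in the laparoscopic group in tumours 0-5cm from the anal verge compared with the TaTME group".
- Item 2, stage of disease, has one: "hypothesis is better disease-free and overall survival in patients with stage III disease compared with patients with stage I or stage II disease". It continues "in the TaTME group as well as the laparoscopic group".

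Three other places bear on the point.

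- Section 5.1 admits "Stage 1-3 according to the AJCC classification including downstaged tumours", as judged on imaging.
- Section 14.2 sets the overall comparison of the arms: "Local recurrence rate, disease-free and overall survival will be compared using the Log-rank test". It adds: "Exploratory analysis of the prognostic effects of various baseline factors on disease-free survival will be carried out through multivariate Cox-regression".
- Section 15.2 lists "Clinical TMN stage" among the items entered at randomisation.

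**The concern.** Two features of item 2 look wrong as written.

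**Direction.** AJCC stages are ordered by extent of disease, and III is the highest stage that section 5.1 admits. The hypothesis expects these patients to live longer, and longer without recurrence, than patients with stage I or II. The protocol offers no reason for this.

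**Contrast.** The hypothesis sets one stage against another and repeats this in each arm. That is a prognostic comparison, and the randomised comparison plays no part in it. It could be confirmed or refuted in both arms whether TaTME is better than, equal to or worse than laparoscopic TME.

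At stake is what the stage subgroup can contribute. If only the stated hypothesis is tested, the trial learns nothing from it about whether the effect of the operation depends on stage. A treatment-by-stage analysis added later would be open to the charge of being post hoc.

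**Working it through.** **The plan's own figure.** Item 2 has no figure of its own. The only computed design figure is the sample size in section 14.1. Its inputs are 5% local recurrence (taken as equal in both arms under non-inferiority), a margin of 4 percentage points, one-sided 2.5%, power 80%, 2:1 allocation and 5% drop-out.

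- Control arm: (1.960 + 0.842)² × 0.05 × 0.95 × (1 + 1/2) / 0.04² = 349.5.
- Total: 3 × 349.5 = 1048.6. Divided by 0.95 this is 1103.7, rounded up to the stated 1104.

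Stage does not enter this calculation, so correcting item 2 leaves it unchanged.

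**The two items of section 14.3 side by side.**

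| | Item 1, height | Item 2, stage |
|---|---|---|
| Groups compared | laparoscopic vs TaTME | stage III vs stage I or II |
| Held fixed | tumours 0-5 cm | treatment arm |
| Uses the randomised comparison | yes | no |
| Expected direction | worse with laparoscopic TME | better in the more advanced stage |

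Swapping the stages in item 2 would repair the last row only. The first three rows would still describe a prognostic comparison.

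**Is the comparison planned elsewhere?** The log-rank comparison in 14.2 is overall, not by stage. The Cox model in 14.2 concerns prognostic effects on disease-free survival; it does not name stage and does not extend to overall survival. Section 14.1 stratifies randomisation on T category (T3a and less, T3b and more), not on stage I to III. No section explicitly plans TaTME versus laparoscopic TME by stage.

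**What the two contrasts could show (illustration).** The protocol gives no survival by stage and no stage mix. The following are assumptions: 3-year disease-free survival of 85% in stage I-II and 65% in stage III, a 60/40 split, proportional hazards, and all randomised patients counted.

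*Contrast as written, laparoscopic arm (369 patients):*
- Hazard ratio, III to I-II: ln(0.65)/ln(0.85) = 2.65.
- Events: 369 × (0.6 × 0.15 + 0.4 × 0.35) = 85.
- z = ln(2.65) × √(85 × 0.6 × 0.4) = 4.4, against the stated direction.

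*The same with 80% and 75%:*
- Hazard ratio: ln(0.75)/ln(0.80) = 1.29.
- Events: 369 × (0.6 × 0.20 + 0.4 × 0.25) = 81.
- z = ln(1.29) × √(81 × 0.24) = 1.1, inconclusive in that arm.

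*Arm-by-stage interaction, both arms (1104 patients).* With 2:1 allocation the variance of a log hazard ratio is about 1/(2/3 × 1/3) = 4.5 divided by the number of events.

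| Assumed DFS, I-II / III | Events, I-II / III | SE of log ratio | 95% limits |
|---|---|---|---|
| 85% / 65% | 99 / 155 | √(4.5/99 + 4.5/155) = 0.27 | ×/÷1.7 |
| 80% / 75% | 132 / 110 | √(4.5/132 + 4.5/110) = 0.27 | ×/÷1.7 |
| 90% / 80% | 66 / 88 | √(4.5/66 + 4.5/88) = 0.35 | ×/÷2.0 |

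Taking off the 5% drop-out divides each SE by √0.95; in the first row it becomes 0.28, and the limits stay near ×/÷1.7.

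**The case against.** The strongest reply is that item 2 is a hypothesis placed under a general announcement of subgroup analyses by stage. It does not prescribe a method. Read with the log-rank comparison in 14.2, a comparison of the arms within each stage is compatible with the text, and its details may sit in a statistical analysis plan that is not at hand. This stands. A reader might infer that the effect of TaTME by stage will never be analysed; the protocol does not support that. It supports only that the one stated hypothesis is not a between-arm one and that no section explicitly plans the comparison.

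A second reply is that the direction is probably a slip of word order, and that the expected direction changes no test statistic, hazard ratio or interval. That is fair, and it limits the importance of the error. It does not repair the contrast.

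Three further inferences are tempting and should not be drawn.

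- *That the hypothesis is almost certain to be rejected in both arms.* This depends on assumed survival: z in the laparoscopic arm is 4.4 under one assumption and 1.1 under another.
- *That the Cox model in 14.2 makes item 2 redundant.* The overlap is partial. That model covers disease-free survival only and does not name stage, so deleting item 2 outright would remove the only stated look at overall survival by stage.
- *That the subgroup will use pathological stage, a post-operative measurement.* Section 14.3 does not say so, section 5.1 ties stage to imaging, and the choice may properly be left to the analysis plan.

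**Conclusion.** The point holds on the wording of 14.3. The only stated hypothesis for stage runs opposite to the ordering of the stages and compares stages within each arm. Testing it would give no information on whether the effect of TaTME relative to laparoscopic TME differs by stage. An unseen analysis plan does not settle this, because the error is in the protocol: an analysis plan that followed the text would carry it forward, and one that corrected it would depart from the protocol.

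The weight is modest. This is one subgroup hypothesis on secondary endpoints. The primary non-inferiority test, the margin and the 1104 patients are unaffected. The finding on direction rests on the meaning of the staging system, and the finding on contrast on the text alone. Neither depends on the assumed survival figures, which serve only to show the precision of the replacement analysis.

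**What to change.** Replace item 2 of section 14.3 with wording to this effect:

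*The effect of TaTME versus laparoscopic TME on disease-free and overall survival will be estimated by clinical stage (I-II versus III) recorded before randomisation, [before / after] neoadjuvant therapy, with a hazard ratio and 95% CI per stage and an arm-by-stage interaction term. The analysis is exploratory.*

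The bracket has to be settled because downstaged tumours are eligible. If a prognostic comparison by stage is still wanted, keep it as a separate descriptive analysis, with worse survival expected in stage III.

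The cost is one paragraph of protocol text, mirrored in the analysis plan. Clinical stage is already entered at randomisation, so no new data item is needed, provided the recorded stage is the one chosen in the bracket. The downside is one more exploratory analysis of limited precision: interaction limits of about ×/÷1.7 to ×/÷2.0 under the assumptions tried above.

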15 ADMINISTRATIVE ASPECTS, MONITORING AND PUBLICATION

15.1 Data collection tools and source document identification

All medical, quality of life and cost data will be collected by the main coordinating centre. Data collection will be facilitated by case record forms for the perioperative period including data on pathology and follow-up. For privacy of patients, no hospital patient identification numbers will be revealed to the coordinating centre. All patient data are coded and identified by means of a randomisation number. This randomisation number does not include initials or date of birth from the patient. The local investigator will have a decoding list with randomisation numbers and hospital patient identification numbers of his patients in the investigator site file.

At each trial operation, the performing surgeon(s) are noted in the case record form. All patients who are considered for operative treatment of rectum carcinoma should be registered, including those who refuse randomisation and those who do not meet inclusion criteria. Brief details of the reasons why patients are not randomised or excluded should be given. The number of patients operated in each centre for rectal cancer will be registered.

15.2 Data collected at randomisation

At randomisation, the clinician will be asked to give the following information through the internet:

- Eligibility criteria fulfilled?
- Randomising physician/surgeon
- Hospital (+ fax number)
- Type of planned surgery
- Patient: gender
- Patient: date of birth
- Clinical TMN stage

15.3 Data collected during preoperative period

- ASA classification
- Length and weight
- Previous abdominal operations
- Medical history
- Date of diagnosis
- Location of the tumour on MRI
- Tumour characteristics
- Proposed type of resection
- Previous radiotherapy of the pelvis
- Preoperative (chemo)radiotherapy

15.4 Data collected during operation

- Code(s) of surgeon(s)
- Date of surgery
- Type and level of resection
- Use of ureter stent
- Presence of radiation damage
- Presence of liver or peritoneal metastases
- Invasion of adjacent organ(s)
- Degree of autonomic nerve preservation
- Type and method of performing anastomosis
- Blood loss in millilitres

-
- 'Skin to skin' operation time
 - Intraoperative complications
 - Wound protection / specimen protection used
 - Reasons for conversion

15.4 Data collected during postoperative period

The postoperative period is defined as the period starting when the patient leaves the operating theatre and ending 90 days postoperatively. The day of operation is considered day 0.

- Postoperative day with fluid intake > 1000 mL resumed
- Postoperative day with passage of first stool or colostomy production in case of no diversion ileostomy
- Day of discharge from hospital
- Complications including death and cause of death and number of reinterventions and reasons of abdominal surgery
- Reason and duration of possible readmission in hospital within 90 days postoperatively
- Analgesic requirement during the first three days
- Duration of absence from work

15.5 Data collected at pathologic anatomical examination

- Macroscopic description
- Histology
- Extent of local invasion
- CRM
- Distal resection margin
- Peritoneal spread
- Metastatic spread
- Synchronous colon pathology
- pTNM
- Tumour regression grade

